2.3 BLOOD SAMPLES FLOW CHART

| PROCEDURE | Pre-screening Period Day -112 to Day -28 | Screening Visit Day -27 to Day -1 | STUDY VISITS | | | | | | | |
|---|---|--------------------------------------|--------------|----------|----------------|---------|----------|----------------|---------------------------------|--------------------|
| | | | Cycle 1 | | | Cycle 2 | | | Cycle 3+ Same as per Cycle 2 | End of Study Visit |
| | | | Visit 1 | | Visit 2 & 3 | Visit 1 | | Visit 2 & 3 | | |
| | | | Day 1 | Days 2-4 | Days 8 & 15 | Day 1 | Days 2-4 | Days 8 & 15 | | |
| Safety Lab Tests (Haematology, Biochemistry, Coagulation) ^a | | X | X | X | X ^c | X | X | X ^c | | X |
| β-HCG Pregnancy Test ^a | | X | X | | | X | | | | X |
| PK Blood sampling ^b | | | X | X | X | X | X | X | | |
| Anti-HIV Antibodies, Anti-HBcAg antibodies, Anti-HBsAg antibodies, HBV-DNA, HCV-RNA Tests | | X | | | | | | | | |
| Immunogenicity Assessment | | X | | | | X | | | | X |
| Free CD205 Assessment | | X | | | | X | | | | X |
| Flow Cytometry for CD205 expression | | X | | | | | | | | |
| DNA sequence of CD205 Assessment | | X | | | | | | | | |

a = For a list of all parameters to be analyzed, please see Table 4.

b = Timings of each blood sampling for PK are listed in the “PK Blood Samples Flow Chart” (sec 2.4).

c= Blood sampling for haematology lab test to be repeated at Visit 2 on Day 11 and at Visit 3 on Day 18 of Cycle 1. Starting from Cycle 2, blood sampling for haematology lab test at Day 11 and Day 18 shall be performed if clinically needed.

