6.2.3 Clinical Experience

The Step 1 (dose escalation in solid tumors) of the MEN1309-01 study, aiming to determine the MTD of MEN1309 in patients with CD205-positive advanced solid tumors is currently ongoing. The first patient has been treated on Oct 03rd, 2017. At the time Protocol Version 3.0 is issued, the dose cohort of 1.60 mg/kg has been successfully completed in Step 1, according to an ATD. As per protocol, the study design changed to an ascending dose cohort of 3+3 upon the occurrence of a DLT of febrile neutropenia which was observed in the first patients treated at 1.60 mg/kg. Consequently, this cohort has been expanded to six patients that have been treated and completed the DLT assessment period. Neutropenia grade 3/4 lasting \leq 7 days (and therefore not qualifying as DLT) was observed in all patient treated at 1.60 mg/kg as the only safety signal of clinical relevance; therefore the next cohort at 2.40 mg/kg dose level (i.e. with 50% higher ascending dose as per CRC decision) is open.

Considering that the dose cohort of 1.60 mg/kg has been successfully completed in Step 1, the first cohort of patients in Step 2 (dose escalation in NHL) is proposed to be open at 0.80 mg/kg (to be confirmed by the CRC).

6.2.4 Translational model-based strategy to support the choice of clinical doses for the first in human study

A translational model-based analysis has also been carried out to support the dosing regimen for the FIH clinical study. Allometric approaches were applied to (i) the monkey PK data to predict the human PK profile; (ii) a population PK/PD model, developed to scale the time-course of MEN 1309-induced neutropenia from monkey to patients; (iii) tumor growth inhibition data in mice, to identify the potential clinical effective dosing regimens. The risk-benefit profile of the proposed dosing schedule was evaluated based on predicted neutropenia and expected antitumor activity in patients.

This translational analysis supports the selected dosing regimen for the FIH study, namely the anticipated therapeutic dose range (ATDR) with 100% dose escalations from 0.05 to 6.4 mg/kg.

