- 1) A starting dose of 0.05 mg/kg which offers a safety factor of 20 to the HNSTD, i.e., higher than the standard safety factor of 6. Moreover, based on allometric PK model, the predicted C_{max} and AUC in human is 35-fold (C_{max}) and 151-fold (AUC) lower than that at the HNSTD. This starting dose was appropriate since no related AEs higher than grade 1 have been observed up to the 0.80 mg/kg in Cohort 5 during DLT observation period;
- 2) In order to mitigate the potential risk of severe and fast progressing infusion reactions, the 1-hour infusion tested in preclinical animal model has been prolonged to 3 hours (up to 6 hours after interruption), with no influence on the expected effective exposure as suggested by PK modelling predictions. Furthermore, mandatory premedication is required, including an antihistamine and an antipyretic, as per local practice, and dexamethasone 20 mg to be administered within 30 to 60 minutes prior to study drug administration. No infusion related reactions have been observed in the first six dose cohorts up to 1.60 mg/kg; thus -under the condition foreseen by the protocol- the risk for infusion reaction remains limited;
- 3) According to PK/PD model-based predictions (data on file), the neutropenia-related risk, as reported in toxicity studies in monkey, is expected to be manageable in humans. The initial data collected during the dose escalation confirmed that neutropenia is the most frequent adverse reaction with MEN1309 (one DLT observed; and six grade 3/4 neutropenia); however up to 1.60 mg/kg dose neutropenia lasted \leq 7 days with spontaneous recovery. Follow-up of neutrophils count value and recovery time-course will be closely monitored in the subsequent cohort(s) of patients by including extra haematological tests prior and before the currently observed nadir of Day 15. If neutropenia will be established as the main limiting toxicity for MEN1309, the CRC - in accordance with the CRC charter, stating that CRC is in charge to drive "any adjustment in premedication and concomitant medication" - will drive the mandatory use, if appropriate, of grow factor support; For the proposed dosing schedule, PK/PD modelling predicts complete recovery from neutropenia for the majority of the patient population, thereby supporting the adequacy of a 21-day inter-dosing interval;

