On Day 18, blood sampling for haematology lab test shall be repeated

NOTE:

Ophthalmic or dermatological visits shall be performed and repeated bi-weekly in case of ocular or dermatological events higher than grade 1 during the study treatment period. The frequency of ophthalmic and dermatological visits can be increased upon Investigator's judgment.

CYCLE 2

Visit 1 (Day 1-Day 4)

Study drug administration will be performed as inpatient treatment. In addition starting from Cycle 2, hospitalization is not mandatory if the patient did not experience any infusion reactions or any adverse events during the administration at Cycle 1.

Day 1

Prior to study drug administration

- Physical examination including vital signs
- ECOG PS evaluation
- Weight measurement
- 12-lead ECG record
- Blood sampling and urine collection for safety lab tests, including β -HCG pregnancy testing

NOTE: safety laboratory tests performed within 24 hours prior to Day 1 are accepted and do not need to be repeated at Visit 1 (Day 1) prior to study drug administration.

- PK blood sampling (pre-infusion)
- Blood sampling for immunogenicity assessment
- Blood sampling for free CD205 assessment
- TLS prophylaxis if applicable (see Appendix II)
- Premedication
- Recording of AEs and change in concomitant medication

Study drug administration

- Study drug administration, given as a 3-hour IV infusion
- Vital signs every 30 minutes during the first hour of study drug administration and then at every hour until the end of infusion. In case of temporary infusion interruption, vital signs should be collected every 15 minutes until the first hour post-infusion re-start and then every hour until the end of infusion (or until 1-hour after the permanent infusion interruption)
- Continuous ECG monitoring during the IV infusion up to 30 minutes after end of infusion and 12-lead ECG record at 30 minutes after end of infusion

NOTE: If ECG monitoring equipment is not available, heart rate should be monitored up to 30 minutes after the end of infusion with final 12-lead ECG record at 30 minutes after the end of infusion.

- PK blood sampling at the end of infusion, and at 1, 2, 4, 6, 8, 10, 12, and 16 hours after the end of infusion

NOTE: PK blood sampling at 10, 12 and 16 hours after the end of infusion is not mandatory

Day 2, Day 3, and Day 4

Post study drug administration

- Physical examination, including vital signs
- Blood sampling and urine collection for safety lab tests

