- The total dose calculated for the first study drug administration has to be also applied for the following ones, provided that the actual patient's weight is within \pm 10% of the weight measured prior to the first study drug administration; otherwise, the total dose to be given shall be calculated based on the weight measured at the corresponding visit.
- The administration of the study drug should only be carried out in a facility in which resuscitation equipment and medical personnel trained in the treatment of anaphylaxis and TLS are immediately available.
- Starting from Cycle 3, the dose of dexamethasone can be adjusted upon Investigator's judgment.
- Starting from Cycle 2, blood sampling for haematology lab test at Day 11 and Day 18 shall be performed if clinically needed.
- If any interruption occurs during MEN1309 infusion at any cycle, an additional blood sampling for PK will be taken at the time of each infusion interruption and just before each infusion resumption.
- ONLY for dose levels higher or equal to 0.8 mg/kg, PK blood samples will be taken at Visits 2 and 3 of each cycle in conjunction with safety blood samples; in case additional samples will be required between study visits for safety reasons, an additional PK sample will be collected.

End of Study Visit (within 6 weeks after the last administered dose or at the time of study withdrawal/treatment discontinuation of study drug)

- Tumor assessment using RECIST v1.1 for Step 1 based on CT scan or MRI and NHL assessment using Cheson Criteria (The Lugano Classification, 2014) for Step 2 based on CT/(PET)-CT scan or MRI
- Physical examination and vital signs
- 12-lead ECG record
- ECOG PS evaluation
- Blood sampling and urine collection for safety lab tests, including β -HCG pregnancy testing
- Blood sampling for immunogenicity assessment
- Blood sampling for free CD205 assessment
- Recording of adverse events and change in concomitant medications

NOTE:

All patients shall undergo the End of Study Visit at the scheduled date within 6 weeks after the last administered dose or at the time of study withdrawal/treatment discontinuation of study drug. Unscheduled assessments showing disease progression and leading to patient's withdrawal can replace the End of Study Visit provided that all assessment/procedures scheduled for this Visit are completed.

Survival Follow-up (up to a period of 12 months after last patient in)

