5. STUDY ENDPOINTS

5.1.1.1. PRIMARY ENDPOINT

Identification of MTD, defined as the highest dose level at which no more than 1 of 6 patients experiences a DLT during the DLT assessment window. Identification of DLT, defined as any of the following adverse drug reactions (ADRs) that is assessed during Cycle 1:

- any grade ≥ 3 cardiac toxicity, new segmental wall-motion abnormalities, or cardiac troponin I or T elevation of grade 3 or higher;
- any grade ≥ 3 elevations in total bilirubin, hepatic transaminases, or ALP levels; in patients with baseline grade 2 hepatic transaminase or ALP levels, an elevation to $\geq 10 \times$ ULN is considered a DLT;
- any grade 3 non-haematologic toxicity lasting > 7 days, (excluding diarrhoea/nausea for which no adequate and optimal therapy has been implemented and alopecia);
- any grade 3 vomiting lasting > 3 days despite adequate and optimal therapy;
- any grade ≥ 4 non-haematologic toxicity;
- any grade 4 thrombocytopenia or anaemia;
- any grade 4 neutropenia lasting > 7 days or febrile neutropenia;

- any treatment delay of > 2 weeks because of delayed recovery from toxicity related to MEN1309 (except for alopecia).

Upon the prophylactic use of growth factor support for neutropenia is made mandatory by the CRC, the DLT criterion related to grade 4 neutropenia has changed as follows:

- any grade 4 neutropenia lasting > 5 days or febrile neutropenia despite the use of growth factor support.

Although dose escalation is primarily based on the incidence of DLTs during Cycle 1, toxicities that meet criteria for DLTs and are observed during Cycle 2 or subsequent cycles are also taken into account for the assessment of toxicity and definition of MTD.

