A Treatment-Emergent SAE is defined as a TESS event classified as serious.

An AE will be classified as related to study drug if causality was recorded as “certainly related”, “probably related”, “possibly related”, “unassessable/unclassifiable”. Missing causality will be considered as related.

An overview of TESS will be provided with the number and percentage of patients reporting an event by cohort and overall for each period. The summaries will be presented for the following categories:

- Any TESS

- Any TESS by grade (<2, >=2)
- Any Serious TESS
- Any mild/moderate/severe TESS
- Any TESS leading to study drug discontinuation
- Any TESS leading to temporary study drug administration interruption
- Any related TESS (by categories)

If a patient has more than one occurrence of a TESS, the patient will be counted only once within that preferred term. The same applies to serious TESSs and drug-related TESSs.

Additionally, the following summaries of TESSs expressed as number and percentage of patients with TESSs will be presented by SOC and PT by cohort and overall, for each period:

- TESS
- Serious TESS
- Serious TESS resulting in death
- TESS of Grade >=2
- TESS of Grade <2
- TESS by intensity (by categories)
- TESS leading to study drug discontinuation
- Serious TESS leading to study drug discontinuation

Drug-related TESSs will be summarized in the same way that TESS as it is described above.

Moreover, the following summary will be presented for drug-related TESS:

- Number of events, number of patients and percentage of patients with DLT by SOC and PT

In the final TFL a summary of TESSs by period and Grade will be reported.

All adverse events (including non-TESS or AEs happening after End of Study Visit of the patient) recorded on the eCRF will be listed. A separate list of serious adverse events will be provided. TESS will be flagged in the listings.

Laboratory data

All laboratory data will be listed.

Clinical chemistry, haematology and urinalysis parameters will be summarized by parameter, visit and cohort using descriptive statistics. The change from baseline will be summarized for each post baseline visit with descriptive statistics by cohort and visit.

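### Day 11 and Day 18 blood counts are mandatory only in Cycle 1, so the SAP's per-cycle adverse-event tables by grade can create or exaggerate a fall in high-grade neutropenia

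*Protocol*

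**What the plan says.** In Cycle 1 the haematology test is "to be repeated at Visit 2 on Day 11 and at Visit 3 on Day 18 of Cycle 1" (Protocol 2.3, footnote c). The Cycle 1 text in Protocol 8.5.1 agrees: "On Day 18, blood sampling for haematology lab test shall be repeated". The notes in the same section then relax the rule: "Starting from Cycle 2, blood sampling for haematology lab test at Day 11 and Day 18 shall be performed if clinically needed". The SAP's blood samples flow chart repeats this. Safety bloods on Days 1-4, 8 and 15 are scheduled in every cycle.

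SAP 6.1.1.2 makes each cycle a separate adverse-event period. It counts patients with treatment-emergent events per period, including by grade, and adds: "In the final TFL a summary of TESSs by period and Grade will be reported". Laboratory parameters are summarised by visit.

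Neutropenia is the toxicity that matters most here. Protocol 6.2.3 reports that grade 3/4 neutropenia lasting at most 7 days "was observed in all patient treated at 1.60 mg/kg as the only safety signal of clinical relevance". Protocol 6.3, item 3, plans closer monitoring of later cohorts "by including extra haematological tests prior and before the currently observed nadir of Day 15".

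Neither document aligns count days across cycles or notes the difference beside the per-cycle tables.

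**The concern.** An afebrile drop in neutrophils is found only if blood is taken while it lasts. If mandatory counts are further apart after Cycle 1, the same true frequency of short episodes yields fewer recorded high-grade events in later cycles. A reader of the per-cycle table would naturally take the fall as neutropenia easing with time on drug. Discretionary Day 11/18 counts do not restore the balance, because they are taken in patients selected on clinical grounds.

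At stake is how the trial's leading toxicity is described over repeated dosing. The tables are descriptive and no formal between-cycle test is planned, so this concerns interpretation and not a decision rule.

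**Working it through.** The plan states no detection rate or incidence by cycle, so there is no figure of its own to reproduce.

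**Schedule (Protocol 2.3 and 8.5.1).** Day 22 stands for the pre-dose count of the next cycle, with visits on their scheduled days.

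- Cycle 1: Days 1-4, 8, 11, 15, 18, which is 8 mandated days. Gaps from Day 8: 3, 4, 3 and 4 days, so the longest is 4.
- Cycle 2 onward: Days 1-4, 8, 15, which is 6 mandated days. Gaps from Day 8: 7 and 7 days, so the longest is 7.

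**Detection rule.** An episode of length d with midpoint m is found if some scheduled day t satisfies |t - m| ≤ d/2. The values of d and the distribution of m are assumptions, because the documents give neither. Discretionary counts are first set to none.

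**Timing spread evenly over Days 8-19 (11 days).** Detection is the length of Days 8-19 covered by the intervals t ± d/2, divided by 11. For d = 3 from Cycle 2, Day 8 covers 8-9.5 and Day 15 covers 13.5-16.5, so (1.5 + 3)/11 = 0.41. In Cycle 1, Days 11 and 18 extend the cover to 8-12.5 and 13.5-19, so (4.5 + 5.5)/11 = 0.91. The ratio is 4.5/10 = 0.45. The other rows follow in the same way.

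| Length (days) | Cycle 1 | Cycle 2+ | Ratio |
|---|---|---|---|
| 3 | 10/11 = 0.91 | 4.5/11 = 0.41 | 0.45 |
| 4 | 11/11 = 1.00 | 6/11 = 0.55 | 0.55 |
| 5 | 11/11 = 1.00 | 7.5/11 = 0.68 | 0.68 |
| 6 | 11/11 = 1.00 | 9/11 = 0.82 | 0.82 |
| 7 | 11/11 = 1.00 | 11/11 = 1.00 | 1.00 |

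**Timing centred on Day 15, the nadir given in Protocol 6.3** (simulation, 400,000 episodes per setting; Cycle 1 vs Cycle 2+).

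| Midpoint | 3 days | 4 days | 5 days |
|---|---|---|---|
| Normal, SD 1 | 0.94 vs 0.87 (0.92) | 1.00 vs 0.95 (0.95) | 1.00 vs 0.99 (0.99) |
| Normal, SD 2 | 0.87 vs 0.55 (0.63) | 1.00 vs 0.69 (0.69) | 1.00 vs 0.81 (0.81) |

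The SD 1 row can be checked by hand. For d = 3 from Cycle 2, P(|m - 15| < 1.5) = 0.87.

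**Sensitivity.**

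- Centring the timing on Day 12 with SD 2 would lower the 3-day ratio to 0.38, but nothing in the documents places the nadir there.
- If each Day 11/18 count is taken with probability 0.5, regardless of the patient's state, the 3-day ratio at Normal(15, SD 2) rises from 0.63 to 0.82. With probability 1 it is 1.00.
- At 7 days or more the ratio is 1.00 in every setting.

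**Effect of the fix.** With both periods restricted to the common days, the two schedules are identical and the ratio is 1.00 for every length and timing.

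**The case against.** The strongest reply is that the effect may be negligible. The stated nadir, Day 15, is counted in every cycle, and with tight timing the loss is 1-8%. Some discretionary counts will be taken. The SAP's defined per-period split is grade 2 or above against below; a grade 2 or worse episode outlasts its grade 4 core and is harder to miss. The by-visit laboratory tables already compare like with like at Days 8 and 15. All of this stands and limits the size. It does not remove the point. The final summary by period and grade leaves its categories undefined. The grade 3/4 episodes on record lasted at most 7 days, the range in which spacing matters. The Day 15 nadir may also have been located under sparser sampling, since extra counts were then being added for later cohorts; that is an inference.

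Two stronger readings are tempting.

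- **MTD.** SAP 5.1.1.1 says that DLT-type toxicities in later cycles "are also taken into account for the assessment of toxicity and definition of MTD", so a reader might infer that the MTD rests on under-detected neutropenia. The documents do not support this. An episode longer than 7 days cannot fall wholly between counts 7 days apart, and febrile neutropenia presents clinically. Only the conditional criterion of more than 5 days, used if growth factor prophylaxis becomes mandatory, leaves a narrow band; a 6-day episode is detected in 0.82 against 1.00 under even timing. How duration is derived from spaced counts is a separate question.
- **Dose.** Because extra counts were planned for later cohorts, a reader might expect an artificial step up above 1.60 mg/kg. Grade 3/4 neutropenia was already recorded in all patients at that dose, so its incidence cannot rise further. Below it, the accelerated titration used single-patient cohorts, with no related event above grade 1 up to 0.80 mg/kg (Protocol 6.3, item 1).

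Finally, a common-day table does not isolate time on drug. Patients with DLT-type toxicity are in general withdrawn (Protocol 8.2.3, with exceptions), and growth factor prophylaxis is barred in Cycle 1 unless the review committee decides otherwise, with no such bar stated for later cycles (8.4.7). Both can lower later-cycle rates. This objection stands and limits what the fix can claim.

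**Conclusion.** The point holds as a matter of unequal ascertainment. Mandatory counts thin out after Cycle 1, the SAP reports by cycle and grade, and nothing aligns the two. The per-cycle adverse-event tables can therefore create or exaggerate a fall in high-grade neutropenia; that they will do so is not established. Under the stated assumptions the apparent fall for a 3-5 day grade 4 episode lies between about 1% and 55%, and it is nil from 7 days up. These figures assume a constant true frequency, on-schedule visits and no discretionary counts, and the documents fix neither episode length nor timing. The Day 8 and Day 15 laboratory tables are unaffected. No distortion of the neutropenia DLT of more than 7 days, or of the dose comparison, is shown. The correction is worth making because it is cheap and removes the one source of imbalance that the analysis can remove.

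**What to change.** In SAP 6.1.1.2 (Adverse Events and Laboratory data):

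1. Add a table of worst laboratory-graded neutrophil grade per cycle, using only days scheduled in every cycle: Days 1-4, 8, 15 and the pre-dose count of the next cycle. State to which cycle each pre-dose count belongs, because the SAP's adverse-event periods end the day before the next administration.
2. Keep the all-counts per-cycle adverse-event table as the safety display, with a footnote that Day 11 and Day 18 counts were mandatory only in Cycle 1.
3. Report the number of Day 11 and Day 18 counts taken in each cycle.
4. Base any between-cycle statement on the common-day table, and say beside it that withdrawal after DLT-type toxicity and growth factor use also differ by cycle.

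The cost is SAP wording, one extra table and a short tally, all from data the protocol already collects. No visit or clinical rule changes. The common-day table will show lower absolute rates for Cycle 1 because it leaves out real counts, so it should not replace the full safety table.

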8.5.2 Sample Handling & Shipping Management

In order to perform pharmacokinetics, immunogenicity, exploratory tests [e.g., free CD205 assessment, DNA sequence of CD205, and CD205 expression by flow cytometry on peripheral blood cells (PBMC)] approximately 15 mL of whole blood need to be collected.

Blood samples will be processed at site or sent to central laboratories (see Laboratory Manual), depending on the type of analysis as detailed below:

- Pharmacokinetics analysis will be performed centrally at [REDACTED]
- Anti-drug antibody for immunogenicity evaluation will be tested centrally at [REDACTED] according to the validated method included in a separate Laboratory Manual.
- Free CD205 assessment will be performed centrally at [REDACTED]
- CD205 expression will be locally assessed at baseline by FACS analysis following the procedure described in a separate Laboratory Manual; the raw data files of these analysis will be uploaded in [REDACTED] to allow the central review on FACS raw data that will be performed at the Clinical [REDACTED]
- DNA sequence of CD205 will be centrally assessed [REDACTED] The assessment will be performed on the PBMC isolated at [REDACTED] (Italy).

Locally assessed slides from archived tissue and new biopsy in conjunction with 5 to 20 unstained slides and/or residual FFPE block will be collected for retrospective central analysis and sent to the following laboratories:

- [REDACTED] for Central IHC analysis of solid tumor samples.
[REDACTED] [REDACTED] for central IHC analysis of NHL samples.

